15.0 RESEARCH PARTICIPANT REGISTRATION AND RANDOMIZATION PROCEDURES

15.1 Research Participant Registration

Confirm eligibility as defined in the section entitled Inclusion/Exclusion Criteria. Obtain informed consent, by following procedures defined in section entitled Informed Consent Procedures. During the registration process registering individuals will be required to complete a protocol specific Eligibility Checklist. The individual signing the Eligibility Checklist is confirming that the participant is eligible to enroll in the study. Study staff are responsible for ensuring that all institutional requirements necessary to enroll a participant to the study have been completed. See related Clinical Research Policy and Procedure #401 (Protocol Participant Registration).

15.2 Randomization

There is no randomization in this study.

16.0 DATA MANAGEMENT ISSUES

A Clinical Research Coordinator(CRC) from the Department of Radiation Oncology (Breast Service) will be assigned to the study. The responsibilities of the CRC include project compliance, data collection, abstraction and entry, data reporting, regulatory monitoring, problem resolution and prioritization, and coordinating the activities of the protocol study team.

The data collected for this study will be entered into a secure database (Clinical Research Database—CRDB). Source documentation will be available to support the computerized patient record.

The data that will be used to assign the next dose level will come from Medidata and CRDB via queries. The queries will normally be run by the CRC; however other members of the research team can be given access to run this particular query. The results of this query will be emailed to the PI and the statistician. The PI must then check the query results to determine if all toxicity data are correct and up-to-date. If the data are correct, the PI will acknowledge this by replying as such to this email. The statistician will use this data and run the TITE-CRM algorithm using scripts created in R to assign the next dose assignment. The statistician will send an email to the PI and CRC providing the MRN, name of the newly registered patient, and dose assignment. Once this is approved and signed by the PI, the CRC will register the patient and dose into CTMS.. If any data are incomplete or incorrect, the PI will inform the CRC. The CRC will correct the data and indicate to the PI when this is done. The process defined above will then run again and the PI will be notified to indicate correctness of the data, the statistician will run the R scripts, and the PI will be asked to approve the dose assignment.

16.1 Quality Assurance

Regular registration reports will be generated to monitor patient accruals and completeness of registration data. Routine data quality reports will be generated to assess missing data and inconsistencies. Accrual rates and extent and accuracy of evaluations and follow-up will be monitored periodically throughout the study period and potential problems will be brought to the attention of the study team for discussion and action. Random-sample data quality and protocol compliance audits may be conducted by the study team, at a minimum of once per year, more frequently if indicated.

16.2 Data and Safety Monitoring

The Data and Safety Monitoring (DSM) Plans at Memorial Sloan-Kettering Cancer Center were approved by the National Cancer Institute in September 2001. The plans address the new policies set forth by the NCI in the document entitled “Policy of the National Cancer Institute for Data and Safety Monitoring of Clinical Trials”, which can be found at <http://cancertrials.nci.nih.gov/researchers/dsm/index.html>.

The DSM Plans at MSKCC were established and are monitored by the Office of Clinical Research. The MSKCC Data Safety and Monitoring Plans can be found on the MSK Intranet

at:

<https://one.mskcc.org/sites/pub/clinresearch/Documents/MSKCC%20Data%20and%20Safety%20Monitoring%20Plans.pdf>

There are several different mechanisms by which clinical trials are monitored for data, safety and quality. There are institutional processes in place for quality assurance (e.g., protocol monitoring, compliance and data verification audits, therapeutic response, and staff education on clinical research QA) and departmental procedures for quality control, plus there are two institutional committees that are responsible for monitoring the activities of our clinical trials programs. The committees : *Data and Safety Monitoring Committee (DSMC)* for Phase I and II clinical trials, and the *Data and Safety Monitoring Board (DSMB)* for Phase III clinical trials, report to the Center's Research Council and Institutional Review Board.

During the protocol development and review process, each protocol will be assessed for its level of risk and degree of monitoring required. Every type of protocol (e.g., NIH sponsored, in-house sponsored, industrial sponsored, NCI cooperative group, etc.) will be addressed and the monitoring procedures will be established at the time of protocol activation

17.0 PROTECTION OF HUMAN SUBJECTS

Participation in this trial is voluntary. All patients will be required to sign a statement of informed consent, which must conform to IRB guidelines.

Inclusion of Women and Minorities: Memorial Sloan-Kettering Cancer Center has filed forms HHS 441 (civil rights), HHS (handicapped individual), 639-A (sex discrimination), and 680 (age discrimination); we also take due notice of the NIH policy concerning inclusion of women and minorities in clinical research populations. Patients of all races will be accepted into the protocol. The proposed study population is as described in section 7.0.

Exclusion of Lactating or Pregnant Women: Children have been excluded from this study. Triple negative breast cancer is an adult cancer. Thus, the relevance of this drug to the pediatric population has not been established. Lactating and pregnant women are also excluded because of potential anti-proliferative effects of chemotherapy that may be harmful to the developing fetus or nursing infant.

Benefits: Taking part in this study may or may not make your health better. We do know that the information from this study will help doctors learn more about rucaparib in combination with radiation therapy as a treatment for cancer. This information could help future cancer patients. You may receive information from physical examinations, laboratory tests, or other testing that is done in this study but these tests may not have any impact on your health.

Costs: The patient will be responsible for the costs of standard medical care, including EKG, scans, drug administration fees and all hospitalizations, even for complications of treatment. Rucaparib will be supplied to patients by Clovis at no cost. Patients will not be responsible

for the costs of blood procurement obtained for research purposes, the digital images, and the questionnaires.

Incentives: No incentives will be offered to patients/subjects for participation in the study.

Alternatives: Patients may be eligible for other investigational studies, or choose standard of care options.

Confidentiality: Every effort will be made to maintain patient confidentiality. Research and hospital records are confidential. Patient's name or any other personally identifying information will not be used in reports or publications resulting from this study. The Food and Drug Administration or other authorized agencies (e.g., qualified monitors) may review patients' records and pathology slides, as required.

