6.0 CRITERIA FOR SUBJECT ELIGIBILITY

6.1 Subject Inclusion Criteria

1. Female, \geq 18 years of age.
2. Non-metastatic, histologically or cytologically-confirmed TNBC (defined as ER <1%, PR <1%, her-2/neu 0-1+ by IHC or FISH-negative or as per MD discretion), with evidence of residual disease in the breast or lymph nodes after neoadjuvant chemotherapy, at the time of definitive surgical treatment.
3. Non-metastatic, histologically or cytologically-confirmed hormone-receptor positive, Her2/neu negative breast cancer (defined as ER >1% or PR >1% AND Her-2/neu 0-1+ by IHC or FISH-negative, or as per MD discretion), with evidence of residual grade 3 invasive breast cancer AND either 1) >5 cm of residual disease in the breast OR 2) ≥ 4 axillary LNs in the axilla after neoadjuvant chemotherapy, at the time of definitive surgical treatment.
4. Definitive surgical treatment with breast-conserving surgery or mastectomy and axillary lymph node evaluation.
5. At least 6-month life expectancy, ECOG Performance status < 2.
6. Willingness to discontinue any cytotoxic chemotherapeutic agents and biologic therapy at least 2 weeks prior to the start of RT.

7. Adequate organ function (assessed within 30 days prior to initiation of protocol treatment, unless otherwise indicated) as follows:

Hematology

Absolute Neutrophil Count (ANC)	$\geq 1500/\text{mm}^3$
Platelet Count	$\geq 100,000/\text{mm}^3$
Hemoglobin	$\geq 9.0 \text{ g/dL}$ (after transfusion if required)

Renal Function

Creatinine	Serum $\leq 1.5 \text{ mg/dL}$ or Creatinine Clearance $\geq 45 \text{ mL/min}^a$
------------	--------------------------------------------------------------------------------------

Hepatic Function

Bilirubin	$\leq 1.5 \text{ mg/dL}^b$
Aspartate Aminotransferase (AST)	$\leq 2.5 \times \text{ULN}$
Alanine Aminotransferase (ALT)	$\leq 2.5 \times \text{ULN}$

ULN = upper normal limit of institution's normal range

- a. If calculated creatinine clearance is $< 45 \text{ mL/min}$, a 24-hour urine collection for creatinine clearance may be performed
- b. Subjects with documented Gilbert's disease may have bilirubin up to 2.5 mg/dL

8. Negative serum pregnancy test within 14 days prior to study treatment if a woman has child-bearing potential. Subjects of child bearing potential are those who have not been surgically sterilized or have not been free from menses for > 1 year.
9. Ability to swallow and retain oral medications.

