10. Written informed consent obtained from subject and ability for subject to comply with the requirements of the study.
11. Female subjects of childbearing potential should be willing to use 2 methods of birth control or be surgically sterile, or abstain from heterosexual activity for the duration of study participation. Should a woman become pregnant while participating on study, she should inform the treating physician immediately.

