6.2 Subject Exclusion Criteria

1. Gross residual tumor on imaging, or positive margins after breast conserving surgery that are un-excised, as radiation dose in the study will be limited to 60 Gy.
2. Complete pathologic response to NAC.
3. Receipt of PARP inhibitor prior to RT.
4. Pregnant or expecting to conceive within the projected duration of the trial, starting with screening visit through 180 days after the last dose of trial treatment.
5. Prior history of radiation therapy to the ipsilateral breast and/or regional nodes is not allowed (prior RT to other sites is permitted).
6. Patients with breast augmentation implants are excluded.
7. History of allergic reactions attributed to compounds of similar chemical or biologic composition to rucaparib.
8. Concomitant anti-neoplastic treatment is not allowed during protocol treatment and should be completed at least 2 weeks prior to commencement of protocol treatment, with resolution of associated acute toxicities. Bisphosphonates are permitted without restriction even during protocol treatment. Maintenance pembrolizumab is permitted during the protocol treatment.
9. Significant comorbidity: Patients with clinically significant and uncontrolled major disease or disorder that could exacerbate potential toxicities, confound safety assessments, require excluded therapy for management, or limit study compliance.
10. Ongoing therapy with other investigational agents. Patients may not be receiving any other investigational agents.
11. Unresolved toxicity from other agents. Patients with unresolved CTCAE v4.03 Grade 3 or greater toxicity from prior administration of another investigational drug and/or anti-cancer treatment are not eligible.

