8.0 PRETREATMENT EVALUATION

All baseline/screening procedures will take place after completion of surgery and within 30 days prior to initiation of protocol therapy, unless otherwise indicated.

- Signed informed consent
- Pathologic confirmation of TNBC or eligible hormone-receptor positive breast cancer
- History and physical examination including height, weight, vital signs (temperature, pulse rate, respiratory rate, blood pressure, pulse oximetry), performance status (ECOG), adverse event monitoring and review of medications
- 12-lead electrocardiogram (EKG)
- Serum pregnancy test for all women of childbearing potential
- CBC with differential and platelet count
- Complete metabolic panel (sodium, potassium, chloride, bicarbonate, BUN, creatinine, glucose, total protein, albumin, bilirubin, alkaline phosphatase, AST, ALT, corrected calcium, magnesium)
- Patient outcomes questionnaire (BCTOS), if applicable
- Patient and Physician Cosmesis evaluations
- Digital Breast Images
- If germline BRCA status is not known at the time of study registration, patients will be referred to their respective Genetics department for evaluation of germline BRCA status and other genes, at the discretion of the treating physician and consulting geneticists.

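### Section 17.0 says lactating women are excluded, but no eligibility criterion in Section 6 and no listed screening item carries that exclusion

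*Combined protocol and SAP*

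**What the plan says.** The human-subjects section (17.0) has a short paragraph on who is kept out of the trial. It names children, pregnant women and lactating women. Of the last two it says: "Lactating and pregnant women are also excluded because of potential anti-proliferative effects of chemotherapy", effects "that may be harmful to the developing fetus or nursing infant". This is a statement of fact with its own rationale, and the nursing infant is named alongside the fetus.

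The operative criteria are in Section 6. Three items bear on reproduction:

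- Exclusion 6.2(4): "Pregnant or expecting to conceive within the projected duration of the trial", running from screening to 180 days after the last dose.
- Inclusion 6.1(8): "Negative serum pregnancy test within 14 days prior to study treatment if a woman has child-bearing potential".
- Inclusion 6.1(11): "Female subjects of childbearing potential should be willing to use 2 methods of birth control or be surgically sterile", or abstain.

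The pretreatment list in Section 8.0 has "Serum pregnancy test for all women of childbearing potential" and nothing on lactation. Table 10A likewise schedules a pregnancy test only.

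For registration, Section 15.1 instructs staff: "Confirm eligibility as defined in the section entitled Inclusion/Exclusion Criteria". It adds that "registering individuals will be required to complete a protocol specific Eligibility Checklist". The checklist itself is not in the document.

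**The concern.** An exclusion protects someone only if the people who register patients are asked to apply it. Here it is stated in the section that describes protections for participants, but it is absent from the list that staff are told to check. A lactating woman with a negative pregnancy test who meets the other criteria satisfies Section 6 as written, while Section 17.0 says she is not to be enrolled.

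If that happened, she would take rucaparib for 9 to 10 weeks, and the precaution that the protocol describes for a nursing infant would not have been applied. Her enrolment would comply with one section and breach another. Section 7.0 opens the trial to multicenter sites as well as the lead institution, so one centre's habits cannot be relied on to fill the gap.

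**Working it through.** No arithmetic applies, because the point concerns the agreement of two sections. The check was to read Sections 6.1, 6.2, 7.0, 8.0, 9.6, Tables 10A and 10B, 15.1, 17.0 and 18.0 for any reference to lactation, nursing or breast-feeding.

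**Step 1. Match each group that Section 17.0 excludes to a criterion.**

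| Group excluded in 17.0 | Matching item in Section 6 | Matching screening item |
|---|---|---|
| Children | 6.1(1), age 18 or over | Demographics (Table 10A) |
| Pregnant women | 6.2(4), with 6.1(8) and 6.1(11) | Serum pregnancy test (8.0, Table 10A) |
| Lactating women | None | None |

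Two of the three groups are carried into Section 6 and one is not.

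**Step 2. Count.** Lactation appears in 0 of 11 inclusion criteria, 0 of 11 exclusion criteria and 0 of the listed screening procedures. In the sections read, it appears only in 17.0.

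**Step 3. Ask whether another criterion covers it indirectly.**

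- A pregnancy test (6.1(8)) does not detect lactation.
- Contraception (6.1(11)) and plans to conceive (6.2(4)) concern a future pregnancy.
- Exclusion 6.2(9) concerns an uncontrolled major disease or disorder, and lactation is neither.

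**Step 4. Follow the cross-references.** Section 17.0 sends the reader to Section 7.0 for the study population. Section 7.0 sends the reader to Section 6.0 for eligibility. Section 15.1 also rests eligibility on the inclusion and exclusion criteria. Each written route ends at a list without the exclusion.

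**Step 5. Compare how the two exposures are handled.** Fetal exposure has a test within 14 days before treatment, two methods of birth control, an exclusion through 180 days after the last dose, and a footnote to Table 10A that strongly encourages monthly testing during treatment and for 6 months afterwards. Infant exposure through nursing, which 17.0 treats as a parallel reason, has no counterpart in any of these places. That pattern suggests an item that was not carried over, and gives no sign of a decision to admit lactating women.

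**Step 6. Look for an effect on the primary analysis.** Section 12.0 makes a patient evaluable for toxicity if she received at least one dose of rucaparib and one fraction of RT. It replaces patients who do not start treatment, or who stop early for reasons other than toxicity. The final posterior estimates use patients who complete the observation period or have a DLT. None of these rules refers to eligibility, and no figure in Section 14.0 depends on it.

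**The case against.** The strongest reply is that Section 17.0 is itself part of the protocol and is plain on the matter, so the exclusion exists and a site that follows the whole document would apply it. That stands. A reader might infer that a site following the plan exactly would enrol a lactating woman, and the documents do not support that. They support the narrower statement that a site relying on Section 6, as Section 15.1 directs, could miss the exclusion.

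A second reply is that the gap may already be closed in practice. A reader might infer that such a woman would pass every check. That cannot be verified, because the Eligibility Checklist is not reproduced and the consent pages were removed before review; either could contain an item. Section 8.0 also requires a history, a physical examination, a medication review and baseline breast images, all of which are occasions when lactation might come to light. This too stands, but none of these procedures asks the question, and a checklist item would have no source criterion in Section 6.

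A third reply is that the case is remote: every patient has had neoadjuvant chemotherapy and definitive breast surgery, and at least three weeks must pass after surgery before protocol therapy (Section 9.6). That is a fair judgement, although the documents give no figure. It limits the number of patients affected and leaves the contradiction in place.

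Finally, a reader might infer that one disputed patient would weaken the DLT data or the MTD estimate, being 1 of the 30 on whom it rests. Section 12.0 rules this out, since evaluability follows from exposure. Her eligibility could be questioned; her contribution to the dose-toxicity estimate could not be questioned on that ground.

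**Conclusion.** The contradiction is real and can be confirmed from the text alone. Section 17.0 states a safety exclusion that the written eligibility criteria and screening procedures do not carry out. It is an inconsistency to be reconciled in the next amendment. It does not call the design into question.

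Its reach is probably very small. That is an assumption based on the population, because the documents give no lactation rate. There is no effect on sample size, dose allocation, DLT evaluability or the MTD estimate. The gain from correcting it is that the protection for a nursing infant described in 17.0 would be applied at registration, and eligibility would have one definition across the protocol. The conclusion about Section 6, Section 8.0 and Table 10A is firm. Whether the omission would go unnoticed at a site depends on a checklist that cannot be seen here.

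**What to change.** Reconcile 6.2(4) with Section 17.0, so that the exclusion which the protocol already states also appears among the exclusion criteria, for example by adding lactation to the existing pregnancy item. Then bring the Eligibility Checklist and the Section 8.0 screening list into line with the amended criterion. First check whether the checklist already has such an item; if it does, only Sections 6.2 and 8.0 need to change.

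The cost is one eligibility line and one question at screening, made in the next amendment. No test or visit is added, the statistical design is unchanged, and any loss of accrual should be negligible if the number affected is as small as assumed.

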17.1 Privacy

MSK's Privacy Office may allow the use and disclosure of protected health information pursuant to a completed and signed Research Authorization form. The use and disclosure of protected health information will be limited to the individuals described in the Research Authorization form. A Research Authorization form must be completed by the Principal Investigator and approved by the IRB and Privacy Board (IRB/PB).

The consent indicates that individualized de identified information collected for the purposes of this study may be shared with other qualified researchers. Only researchers who have received approval from MSK will be allowed to access this information which will not include protected health information, such as the participant's name, except for dates. It is also stated in the Research Authorization that their research data may be shared with other qualified researchers.

17.2 Serious Adverse Event (SAE) Reporting

An adverse event is considered serious if it results in ANY of the following outcomes:

- Death
- A life-threatening adverse event
- An adverse event that results in inpatient hospitalization or prolongation of existing hospitalization
- A persistent or significant incapacity or substantial disruption of the ability to conduct normal life functions
- A congenital anomaly/birth defect
- Important Medical Events (IME) that may not result in death, be life threatening, or require hospitalization may be considered serious when, based upon medical judgment, they may jeopardize the patient or participant and may require medical or surgical intervention to prevent one of the outcomes listed in this definition

Note: Hospital admission for a planned procedure/disease treatment is not considered an SAE.

SAE reporting is required as soon as the participant starts investigational treatment/intervention. SAE reporting is required for 30-days after the participant's last investigational treatment/intervention. Any event that occurs after the 30-day period that is unexpected and at least possibly related to protocol treatment must be reported.

Please note: Any SAE that occurs prior to the start of investigational treatment/intervention and is related to a screening test or procedure (i.e., a screening biopsy) must be reported.

All SAEs must be submitted in PIMS. If an SAE requires submission to the HRPP office per IRB SOP RR-408 'Reporting of Serious Adverse Events', the SAE report must be submitted within 5 calendar days of the event. All other SAEs must be submitted within 30 calendar days of the event.

The report should contain the following information:

- The date the adverse event occurred
- The adverse event
- The grade of the event
- Relationship of the adverse event to the treatment(s)
- If the AE was expected
- Detailed text that includes the following
 - An explanation of how the AE was handled
 - A description of the participant's condition
 - Indication if the participant remains on the study
- If an amendment will need to be made to the protocol and/or consent form
- If the SAE is an Unanticipated Problem

Adverse events of special interest (AESI):

Myelodysplastic syndrome (MDS) and acute myeloid leukemia (AML) are considered adverse events of special interest (AESIs), as these events have been observed in patients exposed to cytotoxic chemotherapy (eg, platinum and anthracyclines) used for treatment of ovarian cancer as well as with PARP inhibitors, including rucaparib. Patients in rucaparib clinical studies diagnosed with MDS or AML had significant confounding risk factors including prior cytotoxic chemotherapy, as well as a deleterious BRCA mutation. Based on these confounding factors, there is insufficient scientific evidence to conclude that MDS and AML are causally related to rucaparib. Clovis has added these potential risks to all Informed Consent Forms (ICFs) / Patient Information Sheets (PISS). AESI's (both serious and non-serious) will be reported to Clovis within 24 hours of awareness and will continue to be reported to Clovis under SAE reporting requirements.

Adverse events (AEs) of pneumonitis have been reported with PARP inhibitor treatment, including in clinical studies evaluating rucaparib. To date, 10 serious clinical study cases and 7 non-serious clinical study cases of pneumonitis have been reported; overall, cases were reported in approximately 0.6% patients. In clinical studies evaluating rucaparib as monotherapy, cases of pneumonitis were reported in approximately 0.1% patients. Currently, however, there is a lack of understanding of a mechanistic

link between pneumonitis and PARP inhibitor treatment. Cases of pneumonitis lack a consistent clinical pattern, and are often confounded with risk factors, such as cancer and/or metastases in lungs, underlying pulmonary disease, smoking history, and/or previous chemotherapy and radiotherapy. To achieve a better understanding of whether there is a relationship between pneumonitis and rucaparib treatment, Clovis has designated pneumonitis as an AESI to gather information on all reported cases. Reportable conditions that fall under this AESI include: pneumonitis, interstitial lung disease, pulmonary fibrosis, acute interstitial pneumonitis, alveolitis necrotizing, alveolitis, hypersensitivity pneumonitis, and organizing pneumonia.

AESIs will be reported using AE and SAE reporting as described above. More information on AESIs for rucaparib is provided in the rucaparib IB.

For IND/IDE protocols: The SAE report should be completed as per above instructions. If appropriate, the report will be forwarded to the FDA by the IND Office.

